### 5. SUBJECT ENROLLMENT

Before subjects begin participation in any study-specific activities/procedures, Amgen requires a copy of the site's written IRB approval of the protocol, informed consent form (ICF) and all other subject information and/or recruitment material, if applicable (see Section 11.2).

All subjects or legally acceptable representatives must personally sign and date the ICF and/or assent before commencement of study-specific procedures. Pediatric subjects must personally sign and date the assent form, as appropriate and if required by the IRB.

A subject is considered enrolled when the investigator decides that the subject has met all eligibility criteria. The investigator is to document this decision and date, in the subject's medical record and in/on the enrollment electronic case report form (eCRF).

Each subject who enters into the screening period for the study receives a unique subject identification number before any study-related activities/procedures are performed. The subject identification number will be assigned manually by the site.

. This number will be used to identify the subject throughout the clinical study and must be used on all study documentation related to that subject.

The subject identification number must remain constant throughout the entire clinical study; it must not be changed after initial assignment, including if a subject is rescreened.

### 6. TREATMENT PROCEDURES

### 6.1 **Classification of Product**

The investigational product for this study is blinatumomab. Blinatumomab will be manufactured and packaged by Amgen Inc. and distributed using Amgen clinical study drug distribution procedures.

The Investigational Product Instruction Manual (IPIM), a document external to this protocol, contains detailed information regarding the storage, preparation, and administration of blinatumomab.

The term "pre-phase therapies" used throughout the protocol refers to other protocol-mandated medication (eg, pre-phase with dexamethasone or intrathecal

Product: Blinatumomab

Date: 20 March 2019 Page 39 of 122

prophylaxis). Pre-phase therapies are commercially available and are not provided or reimbursed by Amgen (except if required by local regulation). The investigator will be responsible for obtaining supplies of these protocol-specified therapies.

#### 6.2 Blinatumomab

Blinatumomab will be supplied as single-use glass injection vials containing a sterile, preservative-free, white to off-white, lyophilized powder for IV administration following reconstitution with sterile water for injection. Sterile water for injection and supplies required for reconstitution and injection of blinatumomab will not be provided to clinical sites.

For information surrounding the use of a continuous infusion pump, refer to Section 6.9.

### 6.2.1 Dosage, Administration, and Schedule

Blinatumomab is administered as a CIVI.

A single cycle of blinatumomab treatment is 6 weeks in duration, which includes 4 weeks of blinatumomab CIVI followed by a 2 week treatment-free interval. The treatment-free interval may be prolonged by up to 7 days, if deemed necessary by the investigator.

Each cohort in the study will receive a combination of 2 dose levels. In the first induction cycle, the initial dose of blinatumomab will be the lower assigned dose level for the first 7 days of treatment (to mitigate for potential CRS and neurologic events associated with introduction to blinatumomab) which then will be escalated (dose step) to the higher assigned dose level starting on day 8 (week 2) through day 29 (week 4). For all subsequent cycles (beginning with the second induction cycle and continuing through consolidation, for applicable subjects) the higher assigned dose level will be the dose for all 4 weeks of continuous treatment.

Blinatumomab will be administered per protocol for a maximum of 5 treatment cycles, or until documented disease progression, intolerable adverse event, or withdrawal of consent.

The drug administration should not be interrupted if possible. In case of infusion interruption due to any technical or logistic reason, the interruption should be as short as possible and the infusion continued at the earliest time possible. Interruptions due to adverse events should be documented and managed per Section 6.5.1. The date and time of infusion bag changes will be collected prior to PK sample collection, all infusion start and stop times, and any dose modifications should be recorded accurately. If the interruption is longer than 4 hours, restart of the infusion should be performed under the

Product: Blinatumomab

Date: 20 March 2019 Page 40 of 122

supervision of the investigator. The subject should be observed overnight for possible side effects after the restart. Administration of dexamethasone premedication as described in Table 4 is recommended. If possible, the infusion duration before and after an interruption should total 28 (± 3) days per treatment cycle.

The daily blinatumomab dose may be up to 10% lower or higher to account for IV handling procedures and possible pump inaccuracies. For dose modifications in case of adverse events see Section 6.5.

A dose of up to 10% higher than the intended dose may not require specific intervention. In case of overdose (> 10% higher dose) or medication error, the infusion should be immediately stopped. Routine supportive and symptomatic care according to standard medical practice is recommended. Once the subject is stabilized and no clinically relevant safety findings due to blinatumomab are observed, resumption of blinatumomab at a correct dose can be considered after consultation with the Amgen medical monitor.

A dose of >10% higher than the intended blinatumomab dose will be considered clinically important and classified as a serious adverse event under the criterion of "other medically important serious event" per Section 9.1.2. If the overdose results in additional adverse event/s, the subject should be followed carefully until all signs of toxicity are resolved and the adverse event/s should be recorded/reported per Section 9 of the protocol.

The dose, start and stop date/time, and lot number of protocol-specified therapy are to be recorded on each subject's eCRF.

The dosing schedule is described by a schema in the protocol synopsis.

### 6.2.1.1 **Blinatumomab Inpatient Dosing**

During cycle 1, inpatient hospitalization will be required for the duration of the DLT observation period (days 1 through 14). During subsequent cycles, inpatient hospitalization is required for the first 48 hours after treatment start and after any dose step to allow close monitoring for potential adverse events associated with T-cell redistribution and potential cytokine release effects triggered by the administration of blinatumomab. It is strongly recommended that subjects remain hospitalized for the remainder of each treatment cycle to ensure subjects may continue to be monitored frequently. The hospitalization time depends on investigator's judgment, as well as safety and tolerability of blinatumomab.

Date: 20 March 2019 Page 41 of 122

Infusion bags will be changed by site nursing personnel trained on the protocol and on the proper administration of blinatumomab. Nurses/physicians adequately trained in emergency medicine should be available for immediate intervention in case of complications.

## 6.2.1.2 Blinatumomab Outpatient Dosing

After a subject meets the minimum criteria for inpatient administration and monitoring as described in the above section, and if a subject is deemed stable by the investigator, subjects may be permitted to leave the clinic periodically. Blinatumomab infusion should continue in the outpatient setting under adequate medical supervision. Outpatient blinatumomab treatment should be allowed only for the clinical sites where outpatient continuous intravenous injection is able to be appropriately managed including coverage for emergencies experienced at night or on holidays. The subject will return to the study site for changes of infusion bags.

In the event of drug interruptions of > 4 hours, the restart of the infusion should be performed in the clinic/hospital under the supervision of the investigator with dexamethasone premedication as described in Table 4.

In case of any adverse event in the outpatient setting, the subject should return to the clinic immediately and the subject should contact the investigator immediately for further instruction on management and assessment of adverse events by the investigator.

## 6.2.2 Phase 1b Dose-cohort Study De-escalation and Stopping Rules

## 6.2.2.1 DLT Criteria

A DLT will be defined as follows:

- Any CTCAE grade ≥ 3 adverse event related to blinatumomab, with exceptions noted below
- Persistent CTCAE grade ≥ 2 non-hematologic adverse events related to blinatumomab that are deemed intolerable by the subject or the treating physician that do not respond to appropriate medical management within 5 days and lead to treatment discontinuation
- Non-hematologic or non-infection adverse events related to blinatumomab leading to treatment discontinuation lasting >14 days are to be considered DLTs by the DRC regardless of their inclusion in Appendix H and Appendix I.

The following will not be considered DLTs:

Specific CTCAE grade ≥ 3 adverse events considered to be consistent with the
current known safety profile of blinatumomab (Appendix H and Appendix I).
However, adverse events in Appendix H and Appendix I which differ substantially
in severity or tolerability compared to the currently known safety profile as
determined by the DRC may be considered a DLT

- CTCAE grade ≥ 3 fever or infection
- Laboratory parameters of CTCAE grade ≥ 3 not considered clinically relevant and/or responding to routine medical management

### 6.2.2.2 DLT Observation Period

The time for the DLT assessment will be the first 14 days of treatment based on the observation that most adverse events are usually observed within a few days of treatment initiation and dose step. If the dose modification per Table 5 is followed, time for the DLT assessment will be the first 21 days. An observed DLT will be attributed to the blinatumomab dose level administered at the time at which the DLT occurred.

## 6.2.2.3 Dose De-escalation Rules

MTD will be defined as the dose level at which  $\leq$  1 of 6 subjects experience a DLT or the maximum administered dose (MAD). The MAD to be tested will be 28 µg/day for adults and 15 µg/m²/day for pediatric subjects. The MTD defines the stopping rules for the study.

Subjects will be enrolled according to the "rolling six" phase 1 design (Skolnik et al, 2008). The decision rules defining the number of subjects enrolled in a dose level are shown in Table 1.

Table 1. Rolling Six Phase 1 Dose De-escalation Decision Rules

# Enrolled	# Subjects with a DLT(s) at end of 14-day Observation Period	# Subjects With Data Pending	Decision
2	2	0	De-escalate*
3	≥ 2	0 or 1	De-escalate*
4	≥ 2	0, 1 or 2	De-escalate*
5	0	0	Select dose for Phase 2
5	≥ 2	0, 1, 2 or 3	De-escalate*
6	0 or 1	0 or 1	Select dose for Phase 2
6	≥ 2	0, 1, 2, 3 or 4	De-escalate*

\* If final dose level has been reached, accrual will be suspended until the 14-day DLT observation period is complete.

Product: Blinatumomab Protocol Number: 2013026

Date: 20 March 2019 Page 43 of 122

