### 2.5 Clinical Hypotheses

The hypothesis for the Phase 1b part of the study is that fewer than 2 out of 6 subjects in both adult and pediatric cohorts will experience a DLT at the administered dose of blinatumomab.

For the Phase 2 part of the study, the hypothesis is that blinatumomab will have clinical activity in the treatment of adult R/R ALL as measured by the rate of CR/CRh\* within 2 cycles. The study design will test a null hypothesis that the level of clinical activity is an ineffective level of 10% or less. The assumed level of effective clinical activity is at least 40%.

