## 6.2.2.3.1 Dose De-escalation Rules for Adult Subjects

During the Phase 1b part, up to 6 subjects will be enrolled in Cohort 1A and receive one to five treatment cycles of blinatumomab at a target blinatumomab dose of 9-28  $\mu$ g/day CIVI, as described in Section 6.2.1. Cohort 2 may open as soon as 5 subjects have completed the DLT observation period with no DLTs, or when 6 subjects have completed the DLT observation period with 0-1 DLT. If  $\geq$  2 subjects experience a DLT during the DLT observation period while receiving 9  $\mu$ g/day during Cohort 1A, the cohort will be closed and Cohort 1C will open at a de-escalated dose level of blinatumomab.

If ≥ 2 subjects experience a DLT during the DLT observation period while receiving 28 μg/day during Cohort 1A, the cohort will be closed and Cohort 1B will open at a de-escalated dose level of blinatumomab. Further, if 1 subject experiences a DLT at 9 μg/day and 1 subject experiences a DLT at 28 μg/day during the DLT observation period in Cohort 1A, the cohort will be closed and Cohort 1D will open at a de-escalated dose level of blinatumomab.

In Cohort 1B, up to 6 subjects will receive a target blinatumomab dose of 9-24  $\mu$ g/day CIVI. Cohort 2 may open as soon as 5 subjects have completed the DLT observation period with no DLTs, or when 6 subjects have completed the DLT observation period with 0-1 DLT. If  $\geq$  2 subjects experience a DLT during the DLT observation period during Cohort 1B, irrespective of dose level, the cohort will be closed and Cohort 1D will open at a de-escalated dose level of blinatumomab.

In Cohort 1C, up to 6 subjects will receive a target blinatumomab dose of 6-28  $\mu$ g/day CIVI. Cohort 2 may open as soon as 5 subjects have completed the DLT observation period with no DLTs, or when 6 subjects have completed the DLT observation period with 0-1 DLT. If  $\geq$  2 subjects experience a DLT during the DLT observation period during Cohort 1C, irrespective of dose level, the cohort will be closed and Cohort 1D will open at a de-escalated dose level of blinatumomab.

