### 6.2.2.3.2 Dose De-escalation Rules for Pediatric Subjects

Up to 6 subjects will be enrolled in Cohort P1 and receive one to five treatment cycles of blinatumomab at a target blinatumomab dose of 5-15  $\mu$ g/m²/day CIVI, as described in Section 6.2.1. If  $\geq$  2 subjects experience a DLT during the DLT observation period while receiving 5  $\mu$ g/m²/day during Cohort P1, the cohort will be closed and Cohort P3 will open at a de-escalated dose level of blinatumomab. If  $\geq$  2 subjects experience a DLT during the DLT observation period while receiving 15  $\mu$ g/m²/day during Cohort P1, the cohort will be closed and Cohort P2 will open at a de-escalated dose level of blinatumomab. Further, if 1 subject experiences a DLT at 5  $\mu$ g/m²/day and 1 subject experiences a DLT at 15  $\mu$ g/m²/day during the DLT observation period in Cohort P1, the

\* Subjects who achieve a complete remission (CR, defined as CR/CRh\*) within 2 induction cycles of treatment may receive consolidation cycles of blinatumomab (up to a maximum of 5 total induction and consolidation cycles, or disease progression, intolerable adverse event or withdrawal of consent)

Date: 20 March 2019 Page 45 of 122

cohort will be closed and Cohort P4 will open at a de-escalated dose level of blinatumomab.

In Cohort P2, up to 6 subjects will receive a target blinatumomab dose of 5-10 µg/m²/day CIVI. If ≥ 2 subjects experience a DLT during the DLT observation period during Cohort P2, irrespective of dose level, the cohort will be closed and Cohort P4 will open at a de-escalated dose level of blinatumomab.

In Cohort P3, up to 6 subjects will receive a target blinatumomab dose of  $3.75-15 \,\mu g/m^2/day \,CIVI$ . If  $\geq 2$  subjects experience a DLT during the DLT observation period during Cohort P3, irrespective of dose level, the cohort will be closed and Cohort P4 will open at a de-escalated dose level of blinatumomab.

In Cohort P4, up to 6 subjects will receive a target blinatumomab dose of  $3.75-10 \,\mu g/m^2/day \, CIVI$ . If  $\geq 2 \, subjects \, experience \, a \, DLT \, during the \, DLT \, observation period during Cohort P4, irrespective of dose level, further enrollment into the study will be suspended until further notice. Additional cohorts may be opened at the discretion of Amgen.$ 

In the expansion cohort, pediatric subjects will receive the dose selected from the Phase1 part (5-15 µg/m²/day) of blinatumomab.

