## 6.2.2.4 Data Review Committee

A DRC will review safety data from each cohort in the Phase 1b part to determine if blinatumomab is safe and tolerable as defined by DLT criteria, taking into account a general benefit: risk assessment. PK data may be reviewed, if available. The DRC will meet to confirm the decision rules and recommendations summarized in Table 2 for adult subjects and Table 3 for pediatric subjects when any of the following criteria are met:

- 2 or more subjects have experienced a DLT in a cohort
- 5 or 6 subjects are enrolled in a cohort and all subjects have completed the 14-day DLT observation period

The DRC will consist of, at a minimum, members from the Amgen and Amgen Astellas Biopharma (AABP) study teams, including at least one clinician, one safety representative, and one investigator participating in the study who has recruited subjects into the cohort under review. Refer to Section 10.3.2 for more information on the scope of the DRC.

Adverse events in Appendix H and Appendix I which differ substantially in severity or tolerability compared to the currently known safety profile as determined by the DRC will be reviewed by the independent DSMB.

<sup>a Subjects who achieve a bone marrow response (blasts ≤ 5%) within 2 induction cycles of treatment may receive consolidation cycles of blinatumomab (up to a maximum of 5 total induction and consolidation cycles, or disease progression, intolerable adverse event or withdrawal of consent)

Date: 20 March 2019 Page 47 of 122

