### 6.5.1.2 **Pediatric Subjects**

Blinatumomab treatment will be interrupted until the following events resolve to ≤ grade 1:

- Grade 2 or higher CRS, tumor lysis syndrome, and DIC/coagulopathy related to blinatumomab
- Grade 2 clinically relevant neurologic event related to blinatumomab, as defined in Appendix I
- Any grade 3 or higher clinically relevant adverse event related to blinatumomab

CTCAE grade 4 adverse events not defined solely based on laboratory parameters at least possibly related to blinatumomab will require permanent discontinuation of blinatumomab. Independent investigator assessment should be used to determine the

Page 52 of 122

Product: Blinatumomab

Date: 20 March 2019 Page 53 of 122

risk:benefit for each individual subject to continue blinatumomab therapy with or without dose reduction or discontinue therapy for:

Grade 4 adverse events that are numerically defined laboratory parameters

 All other grade 3 adverse events and clinically significant laboratory value changes

If the adverse event resolves to  $\leq$  grade 1, blinatumomab may be restarted at the lowest starting dose of the dose cohort for at least 7 days before increasing to a maximum of 15  $\mu$ g/m²/day.

Laboratory assessments will be performed during cycle 1 on days 1 and 2 for the monitoring of tumor lysis syndrome. If a CRS, tumor lysis syndrome, or DIC are observed during week 1, dose modifications will be made as outlined in Table 5. If this dose reduction occurs during cycle 1, the DLT observation period will be extended for an additional 7 days.

Table 5. Treatment Modification for Reversible CRS, Tumor Lysis Syndrome, and DIC

Current Dose	Week 1	Week 2 (Day 8)	Week 3-4 (Day 15)
5 μg/m²/day	3.75 μg/m²/day	5 μg/m²/day	15 μg/m²/day
15 μg/m²/day	5 μg/m²/day	15 μg/m²/day	15 μg/m²/day
10 μg/m²/day	5 μg/m²/day	10 μg/m²/day	10 μg/m²/day

Restart of the infusion should be performed under supervision of the investigator. Before blinatumomab is restarted, premedication with dexamethasone must be administered as described in Table 4. The subject should be observed overnight for possible side effects after the restart.

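### Phase 1b DLT rules contradict each other as written: Table 1 can select a dose before the sixth result is in, and the DLT-evaluable denominator is not defined consistently

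*Protocol*

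**What the plan says.** **Dose selection.** Protocol 6.2.2.3 defines the MTD as a dose level with at most one DLT in six subjects (or the maximum administered dose), and adds that "The decision rules defining the number of subjects enrolled in a dose level are shown in Table 1". The DLT column of Table 1 counts "Subjects with a DLT(s) at end of 14-day Observation Period". The row for six enrolled pairs zero or one DLT with zero or one pending, and the decision is to select the dose.

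Other sections bear on the same decision:

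- Section 2.5 hypothesizes that "fewer than 2 out of 6 subjects in both adult and pediatric cohorts will experience a DLT".
- Section 6.2.2.3.1 (adults) lets Cohort 2 open after five completers without a DLT, or "when 6 subjects have completed the DLT observation period with 0-1 DLT".
- Section 6.2.2.3.2 (pediatric) begins "Up to 6 subjects will be enrolled in Cohort P1" and closes a cohort at two or more DLTs, but has no matching completion condition.
- Section 6.2.2.4 convenes the DRC at two or more DLTs, or when "5 or 6 subjects are enrolled in a cohort and all subjects have completed the 14-day DLT observation period". Section 10.3.2 gives the DRC the choice of Phase 2 dose.
- Section 6.2.2.2 says "If the dose modification per Table 5 is followed, time for the DLT assessment will be the first 21 days". Section 6.5.1.2 says that after such a reduction in cycle 1 "the DLT observation period will be extended for an additional 7 days".

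**Evaluability.** Section 3.4 replaces subjects who are not DLT-evaluable, citing a definition in section 6.2.2, and also replaces those who leave the window early without a DLT. It keeps early leavers with at least 85% of the intended dose as evaluable for safety. Section 10.1.2.2 equates evaluable with having received investigational product. Section 10.2.1 caps each dose level at six evaluable subjects. SAP 7.3 restricts the DLT set to DLT-evaluable subjects without defining them, and SAP 10.5 bases the DLT summary on that set.

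**DLT definition.** Protocol 6.2.2.1 makes a related non-hematologic or non-infection event with discontinuation beyond 14 days a DLT even if it is listed in Appendix H or I. It also lets the DRC count listed events that are atypical in severity or tolerability. SAP section 6 has neither clause and does not mention the appendices.

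**The concern.** A decision table should give the same answer whatever the pending subjects turn out to do. The six-enrolled Select row does not. With one DLT and one pending, a further DLT produces two of six, which Table 1 itself treats as de-escalation.

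The 14-day wording adds a second route to a premature count, because a pediatric subject on the modified schedule is still under DLT observation on days 15 to 21.

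DLT incidence is the Phase 1b primary endpoint. Its denominator depends on whether section 3.4 or section 10.1.2.2 is followed. Its numerator could differ from the DRC's if the SAP's shorter definition is applied on its own.

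**Working it through.** **1. The plan's own figure.** Section 10.2.1 gives 12 to 36 subjects. Each population can pass through at most three successive cohorts (1A, then 1B or 1C, then 1D; likewise P1 to P4): 2 × 3 × 6 = 36. One cohort of six each gives 2 × 6 = 12. Both reproduce. No DLT rate, alpha or power is stated for Phase 1b, so every DLT risk p below is an assumption.

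**2. Does each Table 1 decision survive the pending results?** With d DLTs and m pending, the final count lies between d and d + m. Select is safe if d + m ≤ 1; de-escalate is safe if d ≥ 2. Every listed state passes except one: six enrolled, d = 1, m = 1, where d + m = 2. In that state the chance of ending at two of six is p.

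**3. Size if Table 1 were followed alone, with the sixth subject always pending.** Literal rule: P(at most 1 DLT in 5). All-complete rule: P(at most 1 in 6). The difference is 5p²(1−p)⁴.

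| p (assumed) | literal | all complete | difference |
|---|---|---|---|
| 0.10 | 91.9% | 88.6% | 3.3 points |
| 0.20 | 73.7% | 65.5% | 8.2 points |
| 0.33 | 46.8% | 35.8% | 11.0 points |

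Check at p = 0.20: 5 × 0.04 × 0.4096 = 0.082. If the sixth subject is pending in only 25% or 50% of cohorts (assumed), the difference is 0.25 × 8.2 = 2.0 or 0.50 × 8.2 = 4.1 points.

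**4. The 21-day window.** Table 5, first row: 3.75 µg/m²/day in week 1, 5 from day 8, 15 from day 15. On that schedule none of the first 14 days is at 15 µg/m²/day, so a day-14 count says nothing about the target dose for that subject. Section 2.1.2 reports cytokine release syndrome in 3 of 39 children, 2 of them grade 3. If 2/39 to 3/39 need Table 5 (week-1 onset assumed; tumor lysis and DIC not counted), a six-subject cohort contains at least one such subject with probability 1 − (37/39)⁶ = 27% to 1 − (36/39)⁶ = 38%.

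**5. The denominator.** Take one DLT among six completers. If early leavers without a DLT are replaced and excluded, incidence is 1/6 = 16.7% (exact 95% CI 0.4 to 64.1). If section 10.1.2.2 keeps one such leaver, it is 1/7 = 14.3% (0.4 to 57.9); with two, 1/8 = 12.5% (0.3 to 52.7). Under 10.1.2.2 no dosed subject can be non-evaluable, so the replacement rule in 3.4 has no dosed subject to act on as non-evaluable. Replacing an early leaver in a full cohort would then exceed the cap of six in 10.2.1.

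**6. The SAP definition.** Take a related grade 3 encephalopathy, listed in Appendix H, with discontinuation beyond 14 days. Under protocol 6.2.2.1 it is a DLT, and the text says this overrides the listing. Under SAP section 6 the third bullet makes it a DLT, while the exclusion for events consistent with the known profile could be read to exempt it, and nothing states which prevails. One event classed differently moves a six-subject incidence by 1/6 = 16.7 points. SAP section 11 does not record the abridgement.

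**The case against.** The strongest reply is that Table 1 cannot select a dose by itself. The DRC selects (10.3.2), and one DLT with one pending meets neither of its meeting triggers in 6.2.2.4. The adult text separately requires six completers. Read as a whole, the protocol leaves almost no excess chance of selection. This stands: the differences in step 3 describe Table 1 in isolation.

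A reader might infer that the DRC trigger is the only protection for the pediatric cohorts, because 6.2.2.3.2 has no completion condition. It is not. The MTD definition covers both populations, and 6.2.2.3.2 closes a cohort on DLTs during the observation period, which 6.2.2.2 sets at 14 or 21 days. A late DLT therefore still counts.

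A reader might also take 27% to 38% as an error rate. It is only the chance that a cohort contains a 21-day subject. A wrong count also needs exactly one DLT among the other five (0.41 at p = 0.20) and a late DLT in that subject. Giving that subject the full 0.20 risk in the extra week, 0.27 to 0.38 × 0.41 × 0.20 is about 2% to 3%, and only if the other safeguards fail.

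On evaluability, section 3.4 does supply working rules, and under it alone a replaced subject is not one of the six. That does not remove the conflict, because 10.1.2.2 gives a different rule for the DLT assessment.

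On the SAP, the third bullet still calls such events DLTs, and the DRC clause is discretionary, so its omission removes a power rather than a settled rule. SAP section 8 points to protocol 6.2.2, which contains the full definition, but it does so for de-escalation and stopping rules, not for the DLT summary. This part is real but small.

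**Conclusion.** The inconsistencies are in the text and hold. Table 1 contains one cell whose decision can be reversed by the pending result, and it conflicts with the MTD rule, the adult text and the DRC trigger. Table 1 and 6.2.2.4 use 14 days where 6.2.2.2 and 6.5.1.2 allow 21. Section 10.1.2.2 conflicts with 3.4 on who is DLT-evaluable, and the SAP does not resolve it. The SAP's shortened DLT definition is a lesser instance.

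The measurable effect is on reporting: 16.7% against 14.3% for one DLT with one early leaver, or 16.7 points if one listed event is classed differently in a cohort of six. The 2.0 to 8.2 point excess at p = 0.20 rests on an assumed p, an assumed pending share, and Table 1 being applied alone.

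A reader might infer that a dose was wrongly selected. The documents do not support that: other rules oppose the Table 1 route, the independent safety board was to see cumulative Phase 1b data before Phase 2 enrollment (10.3.3), and the selected doses are already fixed in 6.2.2.3.1 and 6.2.2.3.2. Nothing shows that the one-DLT, one-pending state occurred.

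**What to change.** 1. Table 1, six enrolled: limit Select to zero DLTs with zero or one pending, or one DLT with none pending. Every decision in the table is then unaffected by pending results.
2. Table 1 and section 6.2.2.4: replace the 14-day reference with the subject's own 14- or 21-day window.
3. Replace the parenthesis in section 10.1.2.2 with one definition, used also in section 3.4 and SAP 7.3: a subject is DLT-evaluable if they had a DLT in their window, or received at least 85% of the intended dose in that window without a DLT.
4. Have SAP section 6 cite protocol 6.2.2.1 in full.
5. State which DLT-evaluable set was used in the reported Phase 1b summary, and confirm that the set and the reported DLTs match the DRC's determinations. Section 10.3.4 places Phase 1b summaries in the primary analysis, and the SAP's change log already refers to the report of that analysis, so this is a check and a statement, not a redefinition of results.

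The cost is wording and one review of the Phase 1b records. Under the corrected rule a decision would wait only where a subject with a decisive result is still under observation.
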